9.3.4 Site Visits After Vaccination (Day 8 and Day 29)

Site visits that do NOT include a vaccination will be performed on Day 8 and Day 29. Procedures include diary card review (Day 8 visit only solicited AEs) and blood draw. If applicable, a symptom-directed physical examination (including vital signs) may be performed. Information relating to unsolicited AEs will be obtained by interview at the Day 29 visit. The healthcare professional reviewing these data will discuss the AEs (if any) reported by the subject and will determine if any additional diagnoses and/or AEs are present and/or if concomitant medications and vaccines have been used.

Blood (30-140 mL/visit) should be taken from the subject using an aseptic venipuncture technique for serological immunogenicity testing.

The site should schedule the next site visit or other trial activity with the subject.

The subject will receive a written reminder of the next planned trial activity. The subject will be reminded to contact the site if there are any questions and to contact the site immediately (or as soon as the subject is medically stable) if the subject has a medical condition that leads to a hospitalization or an emergency room visit.

9.3.5 Phone Contact – Safety Call and Final Contact (Day 85)

The final (end of trial) contact will be a phone contact on Day 85.

These calls will facilitate the collection of relevant safety information including concomitant medication, and any AEs/SAEs the subject may have experienced since receiving the trial vaccine. All safety information described by the subject must be written down in a designated location within the source documents.

The investigator must complete the end of trial eCRF page for all subjects who received trial vaccine.

9.3.6 Post-Trial Care

No post-trial care will be provided.

9.4 Biological Sample Retention and Destruction

In this trial, specimens for immune response testing will be collected as described in Section 9.1.6. After blood draw and serum processing, the serum samples will be preserved and retained at a central laboratory that was contracted by the sponsor for this purpose for up to but

not longer than 20 years or as required by applicable law. The sponsor has put into place a system to protect the subject's personal information to ensure optimal confidentiality and defined standard processes for sample and data collection, storage, analysis, and destruction.

Serum samples will be used for the analyses defined in this protocol, but can also, with permission from the subject, be used to assess, improve, or develop tests related to norovirus or the investigational vaccine that will allow more reliable measurement of the response to the investigational vaccine. Serum samples could also be used for further exploratory testing. If the subject does not consent to future testing of samples on the ICF, the subject can still participate in the trial.

Effective

10.0 ADVERSE EVENTS

10.1 Definitions

10.1.1 Adverse Events

An AE is defined as any untoward medical occurrence in a clinical investigation subject administered a trial vaccine; it does not necessarily have to have a causal relationship with trial vaccine administration.

An AE can therefore be any unfavorable and unintended sign (e.g., a clinically significant abnormal laboratory finding), symptom, or disease temporally associated with the administration of a trial vaccine whether or not it is considered related to the trial vaccine.

AEs will be graded by the investigator in the following manner:

Mild	Grade 1	
• Awareness of symptoms that are easily tolerated, causing minimal discomfort and not interfering with everyday activities. Relieved with or without symptomatic treatment.
Moderate	Grade 2	
• Sufficient discomfort is present to cause interference with normal activity. Only partially relieved with symptomatic treatment.
Severe	Grade 3	
• Extreme distress, causing significant impairment of functioning or incapacitation. Prevents normal everyday activities. Not relieved with symptomatic treatment.

10.1.2 Solicited Adverse Events

The occurrence of selected indicators of safety will be measured/collected for 7 days after trial vaccine administration (including the day of administration) and will be recorded on the local and systemic AEs eCRF page as applicable and as listed in [Table 10.a](#).

Any solicited local or systemic AEs observed as continuing on Day 8 trial vaccine administration will be recorded as an AE on the AE eCRF for follow-up. For these persistent/prolonged solicited AEs the end date will be captured on the AE eCRF to permit a separate analysis from the unsolicited AEs (see Section [10.4.2](#)).

Table 10.a Solicited Local and Systemic AEs

Solicited local AEs:	Erythema Induration Swelling Pain
Systemic AEs:	Headache Fatigue Myalgia Arthralgia Vomiting Diarrhea Fever*

Body temperature will be collected and recorded. *Fever is defined as body temperature $\geq 38^{\circ}\text{C}$ (100.4°F) regardless of method used [25].

The severity of solicited safety parameters will be assessed as described in [Table 10.b](#).

Table 10.b **Solicited Safety Parameters**

Adverse Event	Severity Grade	Intensity
Pain at injection site	0	None
	1	Mild: No interference with daily activity
	2	Moderate: Interference with daily activity with or without treatment
	3	Severe: Prevents daily activity with or without treatment
Erythema at injection site ^(a)	0	<25 mm
	1	Mild: $\geq 25 - \leq 50$ mm
	2	Moderate: $>50 - \leq 100$ mm
	3	Severe: >100 mm
Induration at injection site ^(a)	0	<25 mm
	1	Mild: $\geq 25 - \leq 50$ mm
	2	Moderate: $>50 - \leq 100$ mm
	3	Severe: >100 mm
Swelling at injection site ^(a)	0	<25 mm
	1	Mild: $\geq 25 - \leq 50$ mm
	2	Moderate: $>50 - \leq 100$ mm
	3	Severe: >100 mm
Headache	0	None
	1	Mild: No interference with daily activity
	2	Moderate: Interference with daily activity with or without treatment
	3	Severe: Prevents daily activity with or without treatment
Fatigue	0	None
	1	Mild: No interference with daily activity
	2	Moderate: Interference with daily activity
	3	Severe: Prevents daily activity
Myalgia	0	None
	1	Mild: No interference with daily activity
	2	Moderate: Interference with daily activity
	3	Severe: Prevents daily activity
Arthralgia	0	None
	1	Mild: No interference with daily activity
	2	Moderate: Interference with daily activity
	3	Severe: Prevents daily activity
Vomiting	0	None
	1	Mild: No interference with activity or 1 – 2 episodes/24h
	2	Moderate: Some interference with activity or >2 episodes/24h
	3	Severe: Prevents activity, requires outpatient IV hydration
Diarrhea	0	None
	1	Mild: 2 – 3 loose stools/24h
	2	Moderate: 4 – 5 loose stools/24h
	3	Severe: ≥ 6 watery stools/24h or requires outpatient IV hydration
Fever ^(b)	Record body temperature in °C/F	

Abbreviations: h, hour; IV, intravenous.

(a) Subjects are to record greatest surface diameter in mm on the diary.

CONFIDENTIAL

(b) Fever is defined as body temperature greater than or equal to 38°C (100.4°F) regardless of method used [25].

10.1.3 Adverse Events of Special Interest

Not applicable. No adverse event of special interest (AESI) has been identified for this trial.

10.1.4 Medically-Attended Adverse Events

No medically-attended adverse events (MAAEs) will be collected in this trial.

10.1.5 Serious Adverse Events

An SAE is defined as any untoward medical occurrence that:

1. Results in DEATH.
2. Is LIFE THREATENING.
 - The term life threatening refers to an event in which the subject was at risk of death at the time of the event; it does not refer to an event that hypothetically might have caused death if it were more severe.
3. Requires inpatient HOSPITALIZATION or prolongation of existing hospitalization.
4. Results in persistent or significant DISABILITY/INCAPACITY.
5. Leads to a CONGENITAL ANOMALY/FIRTH DEFECT in the offspring of a subject.
6. Is an IMPORTANT MEDICAL EVENT that satisfies any of the following:
 - May require intervention to prevent items 1 to 5 above.
 - May expose the subject to danger, even though the event is not immediately life threatening or fatal or does not result in hospitalization.

10.2 Causality of Adverse Events

Relationship (causality) to the trial vaccine will also be assessed by the investigator. The relationship of each AE to the trial vaccine, including solicited systemic AEs (solicited local AEs are considered as related by default) will be assessed using the following categories:

Related: There is suspicion that there is a relationship between the trial vaccine and the AE (without determining the extent of probability); there is a reasonable possibility that the trial vaccine contributed to the AE.

Not Related: There is no suspicion that there is a relationship between the trial vaccine and the AE; there are other more likely causes and administration of the trial vaccine is not suspected to have contributed to the AE.

10.2.1 Relationship to Trial Procedures

Relationship (causality) to trial procedures should be determined for all AEs.

The relationship should be assessed as related to trial procedure if the investigator considers that there is a reasonable possibility that an event is due to a trial procedure. Otherwise, the relationship should be assessed as not related.

10.2.2 Outcome of Adverse Events

The outcome of AEs can be described as follows:

Resolved: The subject has fully recovered from the event or the condition has returned to the level observed at baseline.

Resolving: The event is improving but the subject is still not fully recovered.

Not resolved: The event is ongoing at the time of reporting and the subject has still not recovered.

Resolved with sequelae: As a result of the AE, the subject suffered persistent and significant disability/incapacity (e.g., became blind, deaf or paralysed).

Fatal: The subject died due to the event. If the subject died due to other circumstances than the event, the outcome of the event per se should be stated otherwise (e.g., not resolved or resolving).

Unknown: If outcome is not known or not reported.

10.3 Additional Points to Consider for Adverse Events

An untoward occurrence generally may:

- Indicate a new diagnosis or unexpected worsening of a pre-existing condition. Intermittent events for pre-existing conditions or underlying disease should not be considered as AEs.

- Necessitate therapeutic intervention.
- Require an invasive diagnostic procedure.
- Require a change in concomitant medication.
- Be considered unfavorable by the investigator for any reason.

Diagnoses vs. signs and symptoms:

- Each event should be recorded to represent a single diagnosis. Accompanying signs (including abnormal laboratory values) or symptoms should NOT be recorded as additional AEs. If a diagnosis is unknown, signs or symptoms should be recorded appropriately as AEs.

Worsening of AEs:

- If the subject experiences a worsening or complication of an AE after administration of the trial vaccine, the worsening or complication should be recorded as a new AE. Investigators should ensure that the AE term recorded captures the change in the condition (e.g., worsening of...).
- If the subject experiences a worsening or complication of an AE, the worsening or complication should be recorded as a new AE. Investigators should ensure that the AE term recorded captures the change in the condition (e.g., worsening of...).

Changes in severity of AEs:

- If the subject experiences changes in severity of an AE, the event should be captured once with the maximum intensity recorded.

Preplanned surgeries or procedures:

- Preplanned procedures (surgeries or therapies) that were scheduled prior to signing of the ICF are not considered as AEs. Complications resulting from any planned surgery should be reported as AEs.

Elective surgeries or procedures:

- Elective procedures performed where there is no change in the subject's medical condition should not be recorded as AEs, but should be documented in the subject's source documents. Complications resulting from an elective surgery should be reported as AEs.

Trial procedures:

- Adverse occurrences related to trial procedures after signing of the ICF are considered as AEs and should be reported as AEs.

AEs occurring during pregnancy:

- AEs that are associated with the pregnancy, or worsened by the pregnancy should be reported, as clinically indicated, using the appropriate pregnancy related terms or indicating the AE is during pregnancy by adding ‘during pregnancy’, ‘in pregnancy’ or ‘antepartum’.

Other:

- If possible, include anatomical location to the AE verbatim.
- Death is the outcome of an AE, not the AE term.
- Cause of death is the AE term.

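### Protocol 10.3 removes intermittent events of pre-existing conditions from the AEs without excepting serious events or those leading to withdrawal, which conflicts with 10.1.1 and 10.1.5 for events outside 10.4.2

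*Protocol*

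**What the plan says.** Protocol section 10.3 lists what an untoward occurrence may generally do. The first item is to "Indicate a new diagnosis or unexpected worsening of a pre-existing condition". The next sentence in that item sets the exclusion: "Intermittent events for pre-existing conditions or underlying disease should not be considered as AEs". Later items include a need for treatment, a change of concomitant medication, and "Be considered unfavorable by the investigator for any reason".

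The definitions are broader. Section 10.1.1 says "An AE is defined as any untoward medical occurrence in a clinical investigation subject administered a trial vaccine" and does not require a causal link to the vaccine. Section 10.1.5 begins "An SAE is defined as any untoward medical occurrence that" and includes among its criteria "Requires inpatient HOSPITALIZATION or prolongation of existing hospitalization". Neither section excepts pre-existing conditions.

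Section 10.4.2 has its own rule for solicited events. Those that continue on Day 8, meet the SAE definition or lead to withdrawal must go on the AE eCRF.

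Section 5.2 makes SAEs, and AEs leading to withdrawal, secondary endpoints from Day 1 to the end of the trial. Section 10.4.4 collects SAEs to Day 85 with a 24-hour report, and section 11.0 has the DMC review them.

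**The concern.** The exclusion sits in the list that explains what an untoward occurrence is, and both the AE and the SAE definitions are built on that term. A site could reasonably read it as limiting both. A subject with known episodic asthma who has an attack of the usual kind and is admitted would then have an SAE under 10.1.5 but no AE under 10.3. Likewise, a subject who leaves the trial because of such an episode would have no AE to count under the withdrawal endpoint.

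The gap looks like an oversight. The two other exclusions in 10.3, for preplanned and for elective procedures, are each followed by a statement that complications are to be reported as AEs. The intermittent-event sentence has no such safeguard.

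An event set aside in this way may bypass 24-hour reporting and DMC review. The SAP cannot recover it, because sections 10.1.4 to 10.1.6 summarise what was recorded. The error can run only toward under-reporting.

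**Working it through.** The plan gives no figure for this point, and the sample size of 80 rests on serum supply, so there is nothing to reproduce. The check compares the texts and then illustrates the scale.

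**Step 1: the same event under each rule.**

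| Event | 10.1.1 / 10.1.5 | 10.3 read literally | 10.4.2 |
|---|---|---|---|
| Non-solicited, usual-pattern flare, admitted | SAE | Not an AE | Does not apply |
| Non-solicited, usual-pattern flare, subject withdraws | AE (withdrawal endpoint) | Not an AE | Does not apply |
| Solicited symptom in the diary window: serious, leading to withdrawal, or continuing on Day 8 | AE, or SAE if serious | Open to argument | Must be entered |
| Flare that departs from the known pattern | AE, or SAE if serious | Untoward (unexpected worsening) | Depends on type |

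Only the first two rows conflict with no rule to settle them.

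**Step 2: how much follow-up 10.4.2 leaves uncovered.** Solicited collection covers Days 1 to 7, and SAE collection covers Days 1 to 85. For symptoms on the solicited list, a new episode starting on Day 8 or later falls outside 10.4.2, which is 85 − 7 = 78 of 85 days. For conditions not on the list, such as asthma or allergy, all 85 days are outside it.

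**Step 3: scale of one omitted SAE.** Inputs: n = 80 (planned number, section 13.3), assuming all are vaccinated and so in the Safety Set. The SAP gives no confidence interval for safety rates. The Clopper-Pearson interval, which it uses for the seroresponse rate, is used here for illustration.

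- Change per subject: 1/80 = 1.25 percentage points.
- x = 1: lower limit 1 − 0.975^(1/80) = 0.03%; upper limit, the 0.975 quantile of Beta(2, 79), = 6.77%.
- x = 0: lower limit 0; upper limit 1 − 0.025^(1/80) = 4.51%.

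**Step 4: are SAE counts likely to be so small?** The documents give no SAE risk, so a range is assumed. The chance of at least one SAE in 80 subjects is 1 − (1 − p)^80:

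| Assumed risk p | P(at least one SAE) |
|---|---|
| 0.5% | 33% |
| 1% | 55% |
| 2% | 80% |
| 5% | 98% |

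At the lower risks few or no SAEs are expected, so one omission could change the report from one SAE to none.

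**The case against.** The case for leaving the text alone has force. Section 10.3 is guidance with hedged wording, while 10.1.5 and 10.4.4 set the SAE definition and the 24-hour rule in their own right. The same 10.3 list counts occurrences that need treatment, need a medication change or are unfavorable in the investigator's view for any reason, and most admissions would qualify. Section 9.1.2 foresees AEs that are exacerbations of an existing problem. Subjects are told to contact the site at once about a hospitalization or emergency visit. Exclusion criteria 15 and 16 remove serious chronic disease, including neurological disease, and any history posing added risk.

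This lowers the likely number of affected events but does not settle the conflict. A hospitalized episode in the known pattern is not an unexpected worsening. Criterion 15 rests on investigator judgment, and milder episodic conditions are not named. No text ranks 10.3 against 10.1.5.

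A reader might infer three stronger points, which the documents do not support:

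- **A contradiction with 10.1.2.** That section requires that "Any solicited local or systemic AEs observed as continuing on Day 8 trial vaccine administration will be recorded as an AE on the AE eCRF", and 10.4.2 repeats it. This is a specific, mandatory rule about continuing solicited events; 10.3 is general guidance about intermittent ones. At most, a recurrent symptom such as headache leaves some room for interpretation. Diary entries reach the eCRF regardless of 10.3 (section 9.3.3), so Day 1 to 7 solicited counts are unaffected.
- **Inconsistency because a headache counts on Day 5 and may not on Day 12.** The first falls in the solicited window and the second does not. That difference is part of the design.
- **A large distortion of the unsolicited-AE rate.** The documents give no prevalence of intermittent conditions, and leaving out ordinary non-serious episodes is a choice that the plan may make.

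**Conclusion.** The concern holds in a limited form. Read literally, 10.3 conflicts with 10.1.1 and 10.1.5 for a serious, usual-pattern episode of a pre-existing condition, and with the section 5.2 endpoint of AEs leading to withdrawal, wherever 10.4.2 does not apply. The SAE, unsolicited-AE and withdrawal-AE endpoints are exposed.

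The expected impact is low. It depends on a site applying 10.3 literally to a serious event or a withdrawal in a healthy adult. That a serious flare would always go unreported is more than the text shows, since several other provisions point the site toward reporting it. If one SAE were lost, the cost is the 1.25-point change worked out above, together with a possible missed expedited report. That size assumes 80 vaccinated subjects and no other SAE.

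**What to change.** Reconcile the sections by adding one sentence after the exclusion in 10.3:

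> *This exclusion does not apply to events that meet the SAE definition in Section 10.1.5 or that lead to withdrawal from the trial.*

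No exception is needed for solicited events continuing on Day 8, because 10.1.2 and 10.4.2 already require their entry. An exception tied to the frequency or severity of past episodes is best avoided, because section 9.1.2 does not say that these are collected.

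The cost is a minor text amendment with its IRB handling, a note to sites, and a few more AE or SAE records. No change to the SAP is needed, since its summaries would take in the added records.

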10.4 Procedures

10.4.1 Collection and Reporting Procedures

All AEs, whether considered related to the use of the trial vaccine or not, must be monitored by the investigator until symptoms subside and any abnormal laboratory values have returned to baseline, or until there is a satisfactory explanation for the changes observed, or until death, in which case a full autopsy report should be supplied, if possible. All findings must be reported on the AE eCRF and on the paper SAE report form* if necessary (see Section 10.4.4). All findings in a subject experiencing an AE must also be documented in that subject’s source documents. Any unsolicited AE will be collected by the subject for 28 days post-dose. AEs leading to withdrawal from the trial are collected throughout the trial.

The following information will be documented for each event:

- Reported term for the AE.
- Start and end date, duration.
- Serious (Y/N).
- Intensity.
- Investigator’s opinion of the causality (relationship) between the event and administration of trial vaccine (related or not related).
- Investigator’s opinion of the causality (relationship) to trial procedure(s), including the details of the suspected procedure.
- Outcome of event.

*SAE reporting will be done with a paper SAE form emailed (encrypted) or faxed [REDACTED]:

10.4.2 Collection and Reporting of Solicited Adverse Events

The occurrence of selected indicators of safety will be collected in the diary card by the subject for 7 days after administration of the trial vaccine (including the day of administration, corresponding to Day 1 and will be recorded on the local and systemic AEs eCRF, as applicable. These will be summarized in the final CSR under the category solicited AEs to differentiate them from unsolicited AEs. Any solicited local (injection site) or systemic AE observed as continuing on Day 8 after the trial vaccine administration will be recorded as an AE on the AE eCRF for follow-up. For these persistent/prolonged solicited AEs, the end date will be captured on the AE eCRF to permit a separate analysis from the unsolicited AEs.

Any solicited AE that meets any of the following criteria must be entered as an AE on the AE eCRF page:

- Solicited local or systemic AEs that lead the subject to withdraw from the trial.
- Solicited local or systemic AEs that lead to the subject being withdrawn from the trial by the investigator.
- Solicited local and systemic AEs that otherwise meet the definition of an SAE (see Section 10.1.2).

10.4.3 Collection and Reporting of Adverse Events of Special Interest/Medically-Attended Adverse Events

AESIs and MAAEs will not be collected.

10.4.4 Collection and Reporting of Serious Adverse Events

Collection of SAEs will commence from the time that the subject is administered the trial vaccine (Day 1). Routine collection of SAEs will continue until the end of the trial (Day 85).

SAEs should be reported according to the following procedure:

A paper SAE report form must be completed, in English, and signed by the investigator immediately or within 24 hours of first onset or notification of the event. The information should be completed as fully as possible but contain, at a minimum:

- A short description of the event and the reason the event is categorized as serious.
- Causality assessment.
- Protocol number.
- Subject identification number.
- Investigator's name.

The paper SAE form must be transmitted within 24 hours to [REDACTED]

